	
Secondary Efficacy Endpoints
 
 
• Proportion of patients achieving <math>\geq 4</math>-point improvement from baseline with respect to the weekly mean of the daily 24-hour Worst Itching Intensity NRS at Week 12 of the Double-blind Treatment Period.
 
• Proportion of patients achieving <math>\geq 3</math>-point improvement from baseline with respect to the weekly mean of the daily 24-hour Worst Itching Intensity NRS at Week 8 of the Double-blind Treatment Period.
 
• Proportion of patients achieving <math>\geq 3</math>-point improvement from baseline with respect to the weekly mean of the daily 24-hour Worst Itching Intensity NRS at Week 4 of the Double-blind Treatment Period.
 
• Proportion of patients achieving <math>\geq 4</math>-point improvement from baseline with respect to the weekly mean of the daily 24-hour Worst Itching Intensity NRS at Week 8 of the Double-blind Treatment Period.
 
• Proportion of patients achieving <math>\geq 4</math>-point improvement from baseline with respect to the weekly mean of the daily 24-hour Worst Itching Intensity NRS at Week 4 of the Double-blind Treatment Period.
 
• Change from baseline in itch-related quality of life at the end of Week 12 of the Double-blind Treatment Period, as assessed by the Skindex-10 Scale total score
 
• Change from baseline in itch-related quality of life at the end of Week 12 of the Double-blind Treatment Period, as assessed by the 5-D Itch Scale total score
 
 
Additional efficacy endpoints are described in Section 8.7.4.
 
Safety Endpoints The safety endpoints used to evaluate the overall safety and tolerability of CR845 will be adverse events, ECG, vital signs, and clinical safety laboratory evaluations.

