  - d. Electrocardiograms must be performed prior to the start of dialysis at Screening, Day 85 (End of Treatment), or at Early Termination visit.
  - e. Pre-dialysis vital signs, including body temperature, heart rate, and blood pressure, will be recorded on Days 1, 15, 29, 43, 57, 71 and 85 (End of Treatment), or at Early Termination visit only when the patient is in a sitting or semi-recumbent position. Heart rate will be measured at each dialysis; if heart rate is clinically significant and outside the prespecified visits per the Schedule of Events, the heart rate will be recorded on the relevant CRF page.
  - f. Pre-dialysis vital signs, including body temperature, heart rate, and blood pressure, will be recorded at the Follow-up Visit (7-10 days after EoT/ET visit). Heart rate will be measured at each dialysis.
  - g. Blood samples for clinical laboratory evaluation will be taken at Screening, and on Days 1 and 85 (End of Treatment), or at Early Termination visit only.
  - h. Training on Worst Itching Intensity NRS will be conducted prior to the first day of the Run-in Period (Day -7).
  - i. Training on Skindex-10 Scale and 5-D Itch Scale may be performed at any time during Screening prior to randomization on Day 1 of the Double-blind Treatment Period.
  - j. Patients will be requested to complete their Worst Itching Intensity NRS worksheets each day at a similar time (either at home on non-dialysis days around the normal start time of their dialysis or in the dialysis unit). On dialysis days, the worksheets will be completed prior to or during dialysis, but must be completed prior to dosing.
  - k. 5-D Itch Scale and Skindex-10 Scale completed on Day 1 and the first visit of Weeks 5, 9 and 11 (on Days 29, 57 and 71) and Week 13 (Day 85). The 5-D Itch Scale will preferably be completed first. If the first visit of the week is missed, the patient may complete the worksheets at their next visit for the same week. The worksheets will be completed prior to or during dialysis (preferably within 1 hour of the dialysis), but must be completed prior to dosing.
  - l. Biomarker samples must be collected prior to the start of dialysis on Day 1 and Day 85.
  - m. Concomitant medications including antipruritic medication will be updated at each dialysis visit during the Double-blind Treatment Period, and until the end of the Follow-up Period.

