##### **6.5.4.1 Adverse Events**

#### **Definition of Adverse Events**

An adverse event is any untoward medical occurrence in a patient or clinical investigational patient administered a medicinal product and which does not necessarily have to have a causal relationship with this treatment. An adverse event can therefore be any unfavorable and unintended sign (including an abnormal laboratory finding, for example), symptom, or disease temporally associated with the use of a medicinal product, whether or not considered related to the medicinal product.

In this study, adverse events will be captured from the time a patient signs the ICF to the Follow-up Visit and include the following:

- Any new sign, symptom, or disease;
- Any new clinically significant or symptomatic laboratory/diagnostic test abnormality;
- Any clinically significant worsening of laboratory/diagnostic test abnormality;

- 
- Any worsening (ie, clinically significant change in frequency, nature, and/or intensity) of a pre-existing condition.

A pre-existing condition is a condition that is present prior to signing the ICF for the study. Pre-existing conditions, such as illnesses, symptoms, reactions, progression of disease states, and other comorbidities, as well as laboratory/diagnostic test abnormalities, will be documented in the patient's record as medical history.

Signs and symptoms will be reported individually as adverse events (non-serious), unless a medical diagnosis was provided. Medical diagnosis, whenever provided, will be reported rather than individual signs and symptoms.

Any adverse event that satisfies any of the seriousness criteria described below will be reported as an SAE using the SAE Report Form, in addition to documenting in the eCRF. Serious adverse events that occurred up to 30 days after the last dose of study drug need to be documented on an SAE Report Form if they are deemed by the Investigator to be "Related" to study drug.

An SAE that occurred after a period of 30 days from the last dose of study drug must be reported when the investigator becomes aware of it and if there is a possible relationship to the study drug or the conduct of the study.

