#### **6.5.4.4 Vital Signs**

Vital signs include sitting or semi-recumbent body temperature, heart rate, and blood pressure and will be measured prior to start of dialysis.

Measurements will be repeated if a value is out of the reference range due to a technical issue, considered abnormal for the patient, or for other medical concerns. Only the repeated measurement will be recorded.

In the event of a clinically significant change in blood pressure and/or heart rate, the Investigator and dialysis staff will evaluate and manage the patient per standard dialysis unit practices with knowledge of the patient’s typical blood pressure and heart rate excursions.

Heart rate will be collected at each dialysis; if clinically significant and outside the prespecified visits per schedule of events, the heart rate will be recorded on the relevant CRF page.

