### **8.8 Safety Analysis**

Analysis of all safety data collected during the Double-blind Phase will be performed on the Double-blind Safety Population. The SAP will provide further detail for the analyses to be applied to each safety parameter, and will also include analyses of safety data collected during the Open-label Extension Phase and during exposure to CR845 during both the Double-blind and Open-label Extension Phases. No statistical hypothesis testing will be carried out and no inferential statistical analysis of the safety parameters will be performed.

The baseline value for all analyses of double-blind safety parameters will be defined as the last value obtained prior to the first dose of double-blind study drug and will include both scheduled and repeat (unscheduled) observations.

---

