#### **8.8.4 Vital Signs and ECGs**

Summary tables will include descriptive statistics for baseline and each postbaseline assessment. Descriptive statistics will be calculated on both the actual score and the change from baseline score. Baseline is defined as the last measurement taken on or prior to the first day of dosing. Note that the Day 1 assessment can be included in the evaluation of baseline if that the assessment is performed prior to dosing.

All vital sign summaries will include the patients in the Double-blind Safety Population who have at least a postbaseline time point (for criteria based on postbaseline assessments) and with both a baseline and at least 1 postbaseline time point (for criteria evaluating changes from baseline).

Clinically notable vital signs will be identified based on the criteria defined in the SAP. For each vital sign parameter, the number and percentage of patients with at least 1 notable value will be tabulated by week and overall for the Double-blind Phase.

All vital signs will be listed in by-patient listings, including visit and collection date/time, and will be sorted by patient identifier and date/time of assessment.

Electrocardiogram results include an overall interpretation of 'normal,' 'abnormal but not clinically significant,' or 'abnormal and clinically significant.' These results will be tabulated at each time point.

Electrocardiogram results will be listed for each visit, including visit, whether ECG was performed (yes/no), explanation (if not performed), assessment date/time, study date, overall interpretation, and relevant medical history number or adverse event number, if deemed a clinically significant abnormality.

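### Section 6.5.4.4 keeps only the repeat of a vital sign even when the first reading was valid, so the notable-value count and listings in 8.8.4 lose readings that the SAP cannot restore

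*Protocol*

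**What the plan says.** Section 6.5.4.4 gives three triggers for repeating a vital sign. The first two stand together: "Measurements will be repeated if a value is out of the reference range due to a technical issue, considered abnormal for the patient". The third is any other medical concern. One recording rule then closes the list for all three: a value is repeated if it is "considered abnormal for the patient, or for other medical concerns. Only the repeated measurement will be recorded".

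Two outputs in Section 8.8.4 use the recorded values. For each parameter, "the number and percentage of patients with at least 1 notable value will be tabulated by week and overall for the Double-blind Phase". In addition, "All vital signs will be listed in by-patient listings, including visit and collection date/time". The cut-offs for a notable value are left to the SAP, which is normal and is not questioned here.

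The Synopsis makes vital signs a safety endpoint: the endpoints "will be adverse events, ECG, vital signs, and clinical safety laboratory evaluations". Section 8.8 limits their use: "No statistical hypothesis testing will be carried out and no inferential statistical analysis of the safety parameters will be performed".

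**The concern.** The three triggers differ in kind. A technical issue means that the first reading is not a measurement of the patient, and discarding it is right. A value thought abnormal, or one that raises a medical concern, may be a correct measurement. Under the abnormality trigger such a reading is removed because of what it showed, which is selection on the outcome being counted.

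Take two patients with the same valid notable reading. If one is re-measured and the repeat falls within limits, that patient contributes no notable value at that visit. If the other's reading is not considered abnormal for that patient, it is not repeated and the value counts. The percentage in 8.8.4 thus reflects repeat practice as well as the patients. At about 95 sites, judgement of what is abnormal will probably vary.

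The SAP can choose cut-offs and summaries, but it cannot analyse a value that the Protocol says not to record.

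**Working it through.** **Step 1: what follows from the text alone.** Call the valid readings taken at a visit F (first) and, where a trigger was met, R (repeat). After a clinical trigger the data hold R only. The recorded readings are a subset of the valid readings taken. A patient with a recorded notable value therefore also has one among all valid readings, but the reverse need not hold. The recorded count is equal to or below the count from all valid readings. This needs no assumption.

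**Step 2: what the Protocol gives for sizing.** Table 2, footnote e, gives six post-baseline days (15, 29, 43, 57, 71 and 85). The Protocol gives no reading variance, cut-off, agreement between paired readings or repeat frequency. There is no figure to reproduce, and everything below is illustration.

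**Step 3: model (all inputs assumed).** Readings have variance 1, and notable means above 1.96, so 2.5% of readings qualify. The correlation between visits is 0.6, and the correlation r between paired readings at one visit is 0.7 to 0.98. A share q of the readings beyond a repeat trigger is repeated and replaced.

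If the trigger equals the notable limit, the recorded share per visit is 0.025 × [1 − q(1 − c)], where c is the chance that the repeat is notable given a notable first reading. Simulation gives c = 0.33 at r = 0.7 and c = 0.81 at r = 0.98.

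- r = 0.7: q = 20% gives 0.025 × (1 − 0.2 × 0.67) = 2.2%; q = 80% gives 0.025 × (1 − 0.8 × 0.67) = 1.2%.
- r = 0.98: q = 20% gives 0.025 × (1 − 0.2 × 0.19) = 2.4%; q = 80% gives 0.025 × (1 − 0.8 × 0.19) = 2.1%.

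**Step 4: patients with one or more notable values over six visits.** These come from simulation with at least 400,000 patients per setting. First readings alone give 9.3% to 9.4%.

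| Repeat trigger | r | 20% repeated | 80% repeated | Difference (points) |
|---|---|---|---|---|
| 1.96 (equals limit) | 0.7 | 8.3% | 4.6% | 3.7 |
| 1.96 | 0.9 | 8.7% | 6.6% | 2.1 |
| 1.96 | 0.98 | 9.1% | 8.1% | 1.0 |
| 1.64 (wider) | 0.7 | 8.5% | 5.7% | 2.8 |
| 1.64 | 0.9 | 9.0% | 8.0% | 1.0 |
| 1.64 | 0.98 | 9.4% | 9.3% | 0.1 |
| 1.28 (wider still) | 0.7 | 8.8% | 6.9% | 1.9 |
| 1.28 | 0.9 | 9.3% | 9.0% | 0.3 |
| 1.28 | 0.98 | 9.4% | 9.4% | 0.0 |

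The trigger matters because, when it equals the limit, a repeat can remove a notable value but never add one. With a wider trigger, some readings below the limit are repeated and come back above it. With a trigger narrower than the limit, notable readings between the two are never replaced, which also shrinks the effect. The Protocol fixes neither the trigger nor the limit. In a planned arm of 175, the largest difference in the table is 175 × 0.037 = 6.5 patients and the smallest is none.

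**Step 5: comparison with true values.** Suppose the gap between paired readings is pure measurement error. The share of patients whose error-free value is notable at some visit is then 2.6% at r = 0.7 and 8.9% at r = 0.98. With the trigger equal to the limit and every notable reading repeated, the recorded share is 3.2% and 7.8%. That is above the truth in the first case and below it in the second. If the gap is real short-term fluctuation, the first readings are the better benchmark.

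**The case against.** Letting a re-measurement supersede an abnormal first reading is a defensible convention, because it reduces noise. It might be inferred that notable values are understated against the truth. Step 5 shows that the documents do not support that: the shortfall is certain only against all valid readings taken.

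It might also be inferred that staff pick which readings to replace. Section 6.5.4.4 makes the repeat mandatory once a trigger is met; judgement enters only in deciding what is abnormal or a concern. The 20% and 80% shares are therefore hypothetical. Nor can one say that readers will be unable to tell a confirmed value from an unrepeated one: the eCRF is not shown and may flag repeats.

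A bias towards one arm is not shown either. The rule is the same in both arms, and Section 6.4.8 blinds patients, Investigators, study staff and the Sponsor.

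The Section 8.8 definition of baseline, which includes scheduled and repeat (unscheduled) observations, might be read as contradicting the rule. It covers all safety parameters and may mean a later unscheduled assessment, so no firm contradiction follows.

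Important changes have other routes. Section 6.5.4.1 captures new signs, symptoms and diseases as adverse events, and also "Any new clinically significant or symptomatic laboratory/diagnostic test abnormality", though that item fits vital signs less directly. Section 6.5.4.4 also records clinically significant heart rates found outside the scheduled visits. These routes limit the harm. They do not return the lost reading to the table or listing.

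**Conclusion.** The point holds as a weakness in data recording. Under the two clinical triggers, a valid first reading is left out of the recorded data, and the notable-value count and listings in Section 8.8.4 are incomplete in a way that the SAP cannot repair. That conclusion rests on the text alone.

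The size is not known. In the illustrations it runs from almost nothing to about 4 percentage points, depending on agreement between paired readings, the share repeated, and where the repeat trigger lies relative to the notable limit. With r of 0.9 or more and a trigger wider than the limit, it is about 1 point or less. The consequence stops at descriptive safety summaries; efficacy, type 1 error and sample size are untouched. It is worth considering as a cheap improvement, not a threat to the trial's conclusions.

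**What to change.** In Section 6.5.4.4, require both readings to be entered in the eCRF with the reason for the repeat. Let the repeat replace the first reading only where a technical failure is documented. The SAP should then state which reading feeds the by-visit summaries, and whether notable values are shown as any valid reading, as confirmed values, or both. When a reading is repeated need not change.

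The cost is one extra eCRF entry per repeat. No further measurement is needed, since both are already taken. The downside is some noisier values in the listings.

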**6.5.4.5 Electrocardiogram**

The 12-lead ECGs will be obtained prior to the start of dialysis and will be read locally by the Investigator or qualified designee. Electrocardiograms read by a qualified designee must be endorsed by the Investigator. Clinically significant abnormalities or worsening findings observed after the first dose of study drug will be reported as treatment-emergent adverse events (TEAEs).

**6.5.4.6 Clinical Laboratory Tests**

Blood samples for clinical laboratory tests including hematology, serum chemistry, and serum pregnancy will be taken prior to dialysis and will be analyzed by a central laboratory. The laboratory tests include the following:

Assessment	Parameters to be analysed
Serum Chemistry	Albumin, Alkaline Phosphatase, ALT/SGPT, AST/SGOT, Bilirubin (Total), BUN, Calcium, Chloride, Creatinine, Glucose, Phosphorus, Potassium, Sodium
Hematology	Basophil %, Basophil (Absolute), Eosinophil %, Eosinophil (Absolute), Hematocrit, Hemoglobin, Lymphocyte %, Lymphocyte (Absolute), MCH, MCHC, MCV, Monocyte %, Monocyte (Absolute), Neutrophil %, Neutrophil (Absolute), Platelet, RDW, Red Blood Cells, White Blood Cells
Serum Pregnancy (females of childbearing potential only)	Human chorionic gonadotropin (HCG)

Processing and shipment of central laboratory samples will be described in the Laboratory Manual.

---

#### **6.5.4.7 Contraception and Pregnancy**

All females of childbearing potential will have blood samples taken at Screening for serum pregnancy testing. Females are considered to be of childbearing potential unless they are:

- Surgically sterile (ie, tubal ligation, bilateral oophorectomy, and/or hysterectomy); or
- Over 55 years of age and have not had a menstrual period in at least 1 year

Once they have consented to participate in the study, all women of childbearing potential will be counseled on the importance of avoiding pregnancy and on the need to practice adequate birth control for the duration of the study, from screening until 7 days after the last dose of study drug.

Medically acceptable methods of birth control include hormonal contraceptives for at least 1 cycle of treatment before study enrollment, an intrauterine device, and barrier with spermicide.

Per inclusion criteria, male patients will agree not to donate sperm after the first dose of study drug until 7 days after the last dose of study drug, and will agree to use a condom with spermicide or abstain from heterosexual intercourse during the study until 7 days after the last dose of study drug. No restrictions are required for a vasectomized male, provided his vasectomy was performed  $\geq 4$  months prior to dosing. If sexual abstinence is chosen by the patient, it must be the preferred and usual lifestyle of the patient and must be practiced for the entire duration of the study.

Women will be counseled to contact the Investigator or his/her staff immediately if pregnancy is suspected. Males will be instructed to report to the Investigator if their partner becomes pregnant during the study.

If a patient becomes pregnant during the Double-blind Treatment Period or Open-label Extension Phase or within 7-10 days after the last dose of study drug, the Investigator will immediately discontinue the patient from the study and contact the Sponsor or designee. Diligent efforts will be made to determine the outcome for all pregnancies in the clinical study. Information on the status of the mother and the child will be forwarded to the Sponsor. Generally, follow-up will occur within 6 to 8 weeks following the estimated delivery date. Any premature termination of the pregnancy will be reported. Both maternal and paternal exposure will be collected. For exposure involving the female partner of a male patient, the necessary information must be collected from the patient while respecting the confidentiality of the partner. A pregnancy report will be completed.

#### **6.5.5 Additional Assessments**

The following additional assessments will be collected during the Double-blind and Open-label Extension Phases:

- 
- Inflammatory biomarkers
  - Missed dialysis visits

#### **6.5.5.1 Inflammatory Biomarkers**

Inflammatory biomarkers, such as interleukin (IL)-6, IL-8, and granulocyte macrophage-colony stimulating factor will be measured, as defined in the statistical analysis plan (SAP). A blood sample of sufficient volume to provide for replicate assays of each biomarker will be collected prior to dialysis per the schedules of events.

Detailed instructions for biomarker sample collection and processing will be provided in the laboratory manual.

#### **6.5.5.2 Missed Dialysis Visits**

The number and reason(s) for missed dialysis will be recorded.

---

## **7.0 Discussion and Justification of Study Design**

### **7.1 Discussion of Study Design and Choice of Control Groups**

The double-blind part of the study was designed to evaluate the efficacy and safety of IV CR845 in hemodialysis patients with moderate-to-severe pruritus. A randomized, double-blind design was chosen to minimize bias. A 12-week duration of treatment was selected to demonstrate durability of the efficacy observed in a prior 8-week treatment study (ie, Study CR845-CLIN2101) and to further evaluate safety during a longer exposure. The primary efficacy endpoint was determined using the Worst Itching Intensity NRS scale, which measures itching intensity over 24 hours. This scale has been validated for this patient population and is identical to the primary efficacy endpoint used in the dose-ranging, Phase 2 study, CR845-CLIN2101.

The open-label part of the study was designed to evaluate the long-term safety of CR845 0.5 mcg/kg IV administered after each dialysis session (generally 3 times per week for up to 52 weeks) in patients who completed the 12-week Double-blind Treatment Period of this study. This design is commonly used in clinical development to obtain long-term safety information. The duration of the study is in accordance with International Council for Harmonisation (ICH) and FDA guidance [[Guidance for Industry February 2016](#)].

